## CLINICAL TRIAL SUMMARY

|  |  |
|--|--|
| Title   | Psilocybin for Treatment-Resistant Depression in Autism: a Pilot Trial with Pre-Post Brain and Cognitive Measurement to Understand Mechanisms  |
| Short Title                                     | PAT-DA   |
| Phase   | Phase I  |
| Methodology                                     | Open-label clinical trial  |
| Clinical trial Duration                         | 33 months to complete all recruitment, study procedures, and data analysis.  |
| Participating site(s)                           | Single-Center  |
| Objectives                                      | To assess the feasibility, tolerability, and efficacy of the use psilocybin alongside psilocybin-assisted therapy (PAT) in autistic adults with treatment-resistant depression (TRD). Furthermore, the use of neuroimaging to explore the mechanisms underpinning antidepressant effects of psilocybin.  |
| Number of Participants                          | Twenty (ten male & ten female) intellectually-able/speech-fluent autistic adults diagnosed with treatment-resistant depression   |
| Study Intervention Reference Therapy/Comparator | 2 doses of psilocybin in conjunction with psilocybin-assisted therapy (PAT), 1 st safety dose of 10mg, 2 nd treatment dose of 25mg   |
| Duration of Intervention                        | 2 dosing sessions 1 week apart, each about 6-8 hours duration  |
| Statistical Methodology                         | Characteristics of the trial cohort will be summarized by mean (SD), median (minimum, maximum). Summary raw scores will be presented at each assessment time both numerically and graphically. A paired t-test will be used to investigate the pre- to post-treatment brain/cognitive metrics and symptom changes. Exploratory analyses will be performed to determine predictors of response including baseline individual features, using logistic regression. Safety profiles will be described by the percentage of each adverse effect. |

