## **2.0 CLINICAL TRIAL OBJECTIVES**

### **2.1 Primary Objective of Main Clinical Trial**

To investigate the feasibility, tolerability, and safety of administering psilocybin in autistic adults with TRD.

Hypothesis 1a (feasibility): We will be able to recruit 20 participants within 21 months with retention >90%.

Hypothesis 1b (tolerability and safety): Adverse events (tolerability) and serious adverse events (safety) will be similar to those reported in the literature on classic serotonergic psychedelics in neurotypical populations.

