## **4.7 Participant Withdrawal Criteria**

### **4.7.1 When and How to Withdraw Participants**

Participants are free to withdraw from participation in the clinical trial at any time.

An investigator may discontinue or withdraw a participant from the clinical trial for the following reasons:

- Pregnancy or if participants cease effective contraception;
- Significant study intervention non-compliance;
- If any adverse event (AE), laboratory abnormality, or other medical condition or situation occurs such that continued participation in the clinical trial would not be in the best interest of the participant; or
- Disease progression which requires discontinuation of the study intervention;
- If the participant meets an exclusion criterion (either newly developed or not previously recognized) that precludes further study participation.

Notably, even if participants cannot complete a post-treatment brain MRI scan (V5) of *the main clinical trial design* or cannot complete any of brain MRI scans of *the optional dense sampling brain MRI data collection* (either for the personal reasons or for an exclusion criterion for the MRI scan), they will not be discontinued/withdrawn from the trial by an investigator.

The reason for participant discontinuation or withdrawal from the study will be recorded within the participant's research record, and/or health record at CAMH.

Participants that are withdrawn from the study will be replaced using the same recruitment methods as outlined in Section 4.2: Participant Recruitment and Screening. The aim is to have 20 participants who complete the study.

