## 5.7 Packaging

The psilocybin will be provided by *Filament Health (Burnaby, British Columbia, Canada)*. The doses of psilocybin used in this study will be *10 mg and 25 mg*. The entire shipment for this trial will be sent in bulk (i.e. *20 capsules x 10 mg each, 20 capsules x 25 mg each*). Psilocybin capsules will be packaged individually in high-density polyethylene bottles (30cc). The dose for each participant will be stored in individual boxes labelled with the protocol number, trial name, lot number, unique box number, and a statement that the drug is for clinical use only. The IP will only be removed from the safe for one participant at a time on the day of their session. For a description of safety reporting, please see Section 8.3.1 of the protocol.

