## 7.0 STATISTICAL PLAN

### 7.1 Sample Size Determination

The proposed sample size of *the main clinical trial* is determined based on the recommendations for pilot trials (Whitehead et al., 2016) and is also a sample size adopted by earlier pilot trials on psilocybin (Carhart-Harris et al., 2016). For the main trial designed with 90% power and two-sided 5% significance, our sample size can detect an effect size (ES) of 0.76 (Cohen's d). We will be able to obtain reasonably reliable estimates on feasibility measures including recruitment (margin of error 15.5%) and retention rate (margin of error 13.1%) and tolerability (margin of error 10.1%). An fMRI study in healthy volunteers reports a very large psilocybin effect size in changes of functional connectivity at Week 1 (ES 1.73) (McCulloch et al., 2022). A meta-analysis of published psilocybin trials reports a large antidepressant effect size in neurotypical populations (ES 0.8) (Galvão-Coelho et al., 2021). Altogether, the proposed sample size of *the main clinical trial* appears to have sufficient power to detect the expected effects.

The proposed sample size of *the optional dense sampling brain MRI data collection* is determined based on a pilot study with the similar dense sampling neuroimaging approach happening at the CAMH (titled "Deriving Everyday Effects of Psychosis - Pilot (DEEP-Pi)"). The Midnight Scan Club dataset, representing the first multi-person deep phenotyping study in healthy individuals, also included a sample of 10 individuals, suggesting that for repeated scanning approaches a sample size of 10 is adequate (Gratton et al., 2018). Nonetheless, we acknowledge this rationale of the sample size decision is arbitrary and recognize this optional dense sampling approach is preliminary and novel.

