### 7.2 Statistical Methods

For Primary Aim (safety/feasibility) of *the main clinical trial*, all participants entering the psilocybin sessions (V3/3) will be included in the analysis of the safety profile and tolerability. Participants completing the two time points of pre- and post-treatment MRI and cognitive tests will be included in the analysis for the neuroscience objective. Participants who at least complete the follow-up at Week 1 (V6) will be included in the final analysis for the exploratory aim of clinical effects, regardless of whether they complete the full protocol. This approach is consistent with the intention-to-treat principle. A paired t-test will be used to investigate the pre- to post-treatment brain/cognitive metrics and symptom changes of *the main clinical trial*. Exploratory analyses will be performed to determine predictors of response including baseline individual features, using logistic regression. Safety profiles will be described by the percentage of each adverse effect.

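### Baseline predictors are to be explored by logistic regression on a binary response in about 20 people, although a linear model of the continuous depression scores already collected would be clearly more powerful

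*Protocol*

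**What the plan says.** Section 7.2 fixes the method: "Exploratory analyses will be performed to determine predictors of response including baseline individual features, using logistic regression". The Clinical Trial Summary repeats it. Neither place names the scale, cut-off or visit that defines response, the number of features, or whether they enter one model.

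The planned sample is "Twenty (ten male & ten female) intellectually-able/speech-fluent autistic adults". For clinical effects, Section 7.2 sets the analysis set: "Participants who at least complete the follow-up at Week 1 (V6) will be included in the final analysis". Withdrawn participants are replaced (Section 4.7.1: "The aim is to have 20 participants who complete the study"), but the drug shipment is "20 capsules x 10 mg each, 20 capsules x 25 mg each" (Section 5.7), so the number dosed stays near 20.

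Continuous scores are already in hand. Section 6.1.1 names GRID-HAMD-17 as an outcome measure. Section 6.2.1 schedules it at V2, V6, V8 and V9 after screening, and BDI-II at V2 and V5 to V9. Section 7.2 itself treats symptom change as continuous for the mean effect: "A paired t-test will be used to investigate the pre- to post-treatment brain/cognitive metrics and symptom changes".

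**The concern.** Logistic regression needs a yes/no outcome. If response is derived from GRID-HAMD-17 or BDI-II in the usual way, a graded score is reduced to two classes before the predictors are examined. In 20 people the smaller class would hold only 5 to 10. The analysis then loses power, its usual tests are poorly calibrated, and odds ratios tend to come out too large. If several features share one model, estimates may not exist at all.

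What is at stake is the reliability of any predictor this pilot reports: real ones are more likely to be missed, and apparent ones to look stronger than they are. This is not a detail that an analysis plan would merely fill in. The Protocol names the model, so a better method would have to depart from it.

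**Working it through.** **The plan's own figure.** Section 7.1 gives a detectable d of 0.76 at 90% power, two-sided 5%. For a paired t-test with n = 20, the noncentrality is 0.76 × √20 = 3.40 and power is 89.7%. The exact detectable d is 0.764. The figure is reproduced, but it concerns the mean change. No figure is given for the predictor analysis.

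**Inputs.** From the Protocol: n = 20, or 18 if retention is 90%; two-sided 5%. Section 1.4 cites response or remission rates of 58% to 75%. Assumed, because the Protocol gives no value: response rates of 50%, 67% and 75% in the simulations; a true predictor–outcome correlation of 0.5 (0.3 as a weaker case); 1, 3 or 5 independent normal predictors, one of them real; a normal continuous outcome.

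**Step 1: information kept after dichotomising.** For response rate p and normal quantile z_p, the large-sample efficiency is φ(z_p)² / [p(1 − p)].

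| p | Efficiency | Loss | Smaller class of 20 |
|---|---|---|---|
| 0.50 | 0.637 | 36% | 10 |
| 0.58 | 0.627 | 37% | 8.4 |
| 0.67 | 0.593 | 41% | 6.6 |
| 0.75 | 0.539 | 46% | 5 |

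The loss passes one half only near p = 0.80 (51%).

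**Step 2: power, one predictor, n = 20, correlation 0.5.**

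| Response rate | Linear | Logistic, Wald | Logistic, likelihood-ratio |
|---|---|---|---|
| 50% | 64% | 29% | 51% |
| 67% | 64% | 21% | 46% |
| 75% | 64% | 13% | 38% |

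A separate simulation gave 15–30% for Wald and 43–52% for likelihood-ratio. The pooled ranges are therefore about 13–30% and 38–52%. With the baseline score added as a covariate, linear regression has about 62%. At a correlation of 0.3, linear power is about 25%, Wald 4–10% and likelihood-ratio 17–22%.

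**Step 3: type I error, one predictor, nominal 5%.** Linear 4–5%, Wald 1–2%, likelihood-ratio 6–7%. With the likelihood-ratio test calibrated to a true 5%, its power at correlation 0.5 is 46%, 38% and 37% at the three response rates.

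**Step 4: sample-size equivalent.** To match linear regression at n = 20, logistic regression needs about 28 to 36 people (likelihood-ratio) or 36 to 42 (Wald). That is an effective loss of 1 − 20/28 = 29% up to 1 − 20/42 = 52%.

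**Step 5: separation, correlation 0.5.**

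| Predictors in one model | n = 20 | n = 18 |
|---|---|---|
| 1 | 0.1–1.4% | 0.7–2.1% |
| 3 | 2–12% | 5–16% |
| 5 | 13–29% | 20–42% |

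**Step 6: size of estimates.** At n = 20 and 60% response, the implied logit slope is about 0.95. The median estimate is 1.07 with one predictor and 1.37 with five.

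**The case against.** Several stronger readings are tempting, and the document does not support them.

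- A reader might infer that most of the information is lost. At response rates of 50% to 75% it is 36% to 46%.
- A reader might infer that separation is likely. That needs several features in one model. Section 7.2 speaks of predictors and features in the plural, and Section 6.1.1 groups AQ-12, RBQ-2A and CAT-Q as baseline autistic features, but nothing says they are fitted together. One at a time, the risk is about 1% or less at n = 20.
- A reader might quote only the Wald comparison. The Protocol names no test, and against the likelihood-ratio test the gap is about half as wide or less.
- A reader might count the missing response definition as a fault. A statistical analysis plan may supply it, and it need not come from a depression score: Section 6.1.1 also lists the CGI-I, a seven-point rating.
- A reader might take finding predictors for a larger trial as a stated aim. Section 1.4 says something similar only of candidate brain mechanisms, and no objective in Section 2 mentions predictors.

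It is also fair that the correlation of 0.5 is an assumption. At 0.3 neither method is adequate, so changing the model does not rescue the aim for modest predictors. Section 2.3 disclaims power for efficacy, and the mean symptom change is analysed continuously in any case.

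What stands of this limits the size and priority of the point. It does not remove it. No cut-off restores the information lost, the linear model had higher power in every scenario examined, and its type I error is close to nominal where neither usual logistic test is.

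**Conclusion.** The point holds in a moderate form. The Protocol commits to a less efficient model than its own data allow. With one predictor at a true correlation of 0.5, the linear model gains roughly 13 to 26 percentage points over the likelihood-ratio test in the simulation tabulated (64 − 51 to 64 − 38) and about 35 to 51 over the Wald test (64 − 29 to 64 − 13). These figures rest on an assumed correlation, assumed response rates of 50% to 75%, normal scores and about 20 people analysed. They also presume that response would be cut from a continuous score. The separation concern is conditional on joint fitting. Because the analysis is exploratory and no primary conclusion depends on it, the change is worth making but not urgent.

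**What to change.** Replace the logistic-regression sentence in Section 7.2 and in the Clinical Trial Summary. The main exploratory predictor analysis becomes a linear regression of the V6 GRID-HAMD-17 score on the V2 score plus one baseline feature at a time, from a short list fixed in advance. BDI-II serves as support. Report every listed feature's slope with its 95% confidence interval, labelled hypothesis-generating.

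If a binary response is wanted, define it and show it descriptively. If it is modelled, use Firth-penalised logistic regression with a single predictor.

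The cost is one sentence in two places, with no new visit, instrument or participant. The downside is that results are read as scale points per unit of predictor rather than as odds of response.

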## 8.0 SAFETY AND ADVERSE EVENTS

### 8.1 Definitions

#### Adverse Event

An **adverse event** (AE) is any untoward medical occurrence in a research participant administered an investigational product and which does not necessarily have a causal relationship with this treatment. An adverse event (AE) can therefore be any unfavourable and unintended sign (including an abnormal laboratory finding), symptom, or disease temporally associated with the use of a medicinal (investigational) product, whether or not related to the investigational product.

AE severity can be defined as:

- *Mild*: discomfort noticed but no disruption of normal activity
- *Moderate*: discomfort sufficient to reduce or affect normal daily activity
- *Severe*: interferes significantly with the participant's normal activity or course of illness

#### Serious Adverse Event

A **serious adverse event** (SAE) is any AE that is:

- Fatal;
- Life-threatening;
- Requires or prolongs hospital stay;
- Results in persistent or significant disability or incapacity;
- A congenital anomaly or birth defect; or
- An important medical event (events that may not be life threatening but are of major clinical significance, such as a drug overdose or seizure that did not result in in-patient hospitalization).

#### Adverse Drug Reactions

An adverse drug reaction is any noxious, unintended or undesirable response to a medicinal product related to any dose.

#### Unexpected Adverse Reactions

An adverse reaction, the nature or severity of which is not consistent with the applicable product information (e.g. Investigator's Brochure).

#### Adverse Event Collection Period

AEs occurring as of the first study visit (V1) through the final study visit (V9) will be collected. AEs recorded during this period will be followed through to resolution, or until the event is assessed as chronic or stable.

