### Medication Tapering Risks

There will be a washout period of a minimum of 2 weeks (4 weeks for fluoxetine) for participants taking any concomitant medications. Withdrawing from medications may result in difficulty sleeping, nausea, diarrhea, flu-like symptoms, and jitters. These symptoms are not dangerous and usually pass in a few days. In addition, tapering off antidepressant medications can result in the worsening of a participant's symptoms. During the tapering period, the participant will be seen clinically by the study physician.

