## **3.2 Primary Endpoints**

The primary safety endpoints of the main clinical trial design will be evaluated using standardized adverse events monitoring at all time points. Adverse event monitoring will be prioritized to closely and thoroughly evaluate the acute and sub-acute psychological safety profile. Blood pressure and heart rate will be examined before (V2) and during the psilocybin dosing sessions (V3/V4). Constant observation by therapists will monitor for adverse events during the dosing sessions. An on-call psychiatrist will be available at all times to further assess as needed for acute concerns. The safety endpoint is the number and severity of adverse events reported throughout the duration of the trial.

Feasibility endpoints of the main clinical trial design include the recruitment and retention rates. Dropout rates during three periods will be evaluated, namely: 1) screening period in which the participant undergoes medication tapering and washout; 2) during the acute course of the study intervention; and 3) during the follow-up after the intervention. Throughout all three periods, we will also evaluate adverse events including psychological distress and serious adverse events (e.g., hospitalization, suicide attempt, death).

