#### Preexisting Condition

A preexisting condition is one that is present at the start of the clinical trial. A preexisting condition will be recorded as an adverse event if the frequency, intensity, or the character of the condition worsens during the study period. At the Screening Visit (V1), any clinically

significant abnormality will be recorded as a preexisting condition in the participant's CRF. Where applicable and at the consent of the participant, additional information from the participant's healthcare provider including medical records, may be requested. Throughout the clinical trial, any new clinically significant findings/abnormalities that meet the definition of an adverse event will also be recorded and documented as an adverse event.

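### The whole-trial safety endpoint and the Section 7.2 percentages put antidepressant-taper symptoms into the adverse-event figures that hypothesis 1b compares with psychedelic trials

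*Protocol*

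**What the plan says.** Four statements in the protocol fix what is counted.

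- **Window** (Section 8.1, Adverse Event Collection Period): "AEs occurring as of the first study visit (V1) through the final study visit (V9) will be collected". V1 is the screening visit, before any taper and before any psilocybin.
- **Reference state** (Section 8.1, Preexisting Condition): "A preexisting condition is one that is present at the start of the clinical trial", and "A preexisting condition will be recorded as an adverse event if the frequency, intensity, or the character of the condition worsens during the study period". Preexisting findings are recorded at V1.
- **Endpoint** (Section 3.2): "The safety endpoint is the number and severity of adverse events reported throughout the duration of the trial".
- **Summary** (Section 7.2): "all participants entering the psilocybin sessions (V3/3) will be included in the analysis of the safety profile and tolerability", and "Safety profiles will be described by the percentage of each adverse effect".

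Two further statements show why this matters. Section 1.6 (Medication Tapering Risks) warns: "Withdrawing from medications may result in difficulty sleeping, nausea, diarrhea, flu-like symptoms, and jitters". It adds that depression may worsen. Hypothesis 1b (Section 2.1) predicts that adverse events and serious adverse events "will be similar to those reported in the literature on classic serotonergic psychedelics in neurotypical populations".

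**The concern.** Between V1 and the first dose, participants on antidepressants, antipsychotics or methylphenidate must stop them (Section 5.6). The protocol expects that step to cause symptoms. If those symptoms are counted in the same percentage as effects that follow dosing, the figure describes withdrawal plus psilocybin, and hypothesis 1b compares it with a literature on psychedelics.

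Effects that both causes can produce would look more frequent than they are after psilocybin. The protocol says it knows of no earlier psilocybin trial in autistic people (Section 1.4), so these percentages are among its main products and are likely to be quoted.

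**Working it through.** **1. Follow one participant through the rules.** Suppose a participant has nausea in the first taper week, it resolves before V2, and there is none after either dose.

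- Window, V1 to V9: the event is inside it.
- Reference, start of trial: the nausea was absent at V1, so it is new.
- Endpoint, whole trial: it counts.
- Safety population: the participant was dosed, so is included.
- Summary, percentage of each adverse effect: the participant adds one to nausea.

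No stated step removes the event. The same happens to poor sleep that is mild at V1, worse at V2 because of the taper, and unchanged after dosing. It has worsened since the start of the trial but not since V2.

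**2. Does the protocol mean pre-dose events to count?** Its text points both ways.

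- *Against:* Section 8.1 defines an adverse event in a participant to whom the investigational product has been administered. Read literally, a taper symptom before V3 does not qualify.
- *For:* the window opens at V1; the schedule in Section 6.2.1 has adverse-event and UKU review at V1, in the taper and at V2; Section 3.2 evaluates adverse events during the taper; and Section 4.6 expects adverse events in screen failures, who are never dosed.

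Most of the text treats taper events as adverse events. The definition does not fit and needs reconciling.

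**3. Size.** The protocol gives no adverse-event rates, so the rates here are assumptions. Let *p* be the proportion of dosed participants with the effect after dosing, and *t* the proportion of all dosed participants with it during the taper. If the two are independent,

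reported = 1 − (1 − p)(1 − t), with excess over p = t(1 − p).

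With p = 20% and 20 participants (4 with the effect after dosing):

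| t | Reported | Excess | Expected count of 20 | If fully overlapping / never overlapping |
|---|---|---|---|---|
| 10% | 1 − 0.8 × 0.9 = 28% | 8 points | 5.6 | 20% / 30% |
| 20% | 1 − 0.8 × 0.8 = 36% | 16 points | 7.2 | 20% / 40% |
| 30% | 1 − 0.8 × 0.7 = 44% | 24 points | 8.8 | 30% / 50% |

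The last column drops independence: the lower bound is the larger of p and t, the upper bound is p + t. With p and t each ranging over 10% to 50%, the excess under independence runs from 0.1 × 0.5 = 5 points to 0.5 × 0.9 = 45 points.

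Because *t* is taken over all dosed participants, it equals the share who tapered times the rate among them. If half tapered and 20% of those had the symptom, t = 0.5 × 0.2 = 10%, giving 28%. If nobody tapered, t = 0 and there is no excess.

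**4. Against the plan's own precision.** Section 7.1 gives a tolerability margin of error of 10.1% without stating the rate or the number behind it. The usual formula, 1.96 × √(p(1 − p)/n), gives 9.55% for p = 95%, n = 20, and 10.07% for p = 95%, n = 18. So the figure is plausible, but its inputs cannot be confirmed. Of the three excesses in the table, 8 points is below 10.1 points, while 16 and 24 are above it.

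**The case against.** **The SAP may deal with this.** Table layout and the definition of a treatment-emergent event usually sit there, and it is not at hand. This stands for table layout. It does not cover the endpoint sentence in Section 3.2, which is whole-trial in the protocol itself. An SAP that counted only post-dose events would depart from it.

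**Section 3.2 names the taper as its own period.** It does, and it says that adverse events will be evaluated throughout all three periods. But the periods are introduced for dropout rates, the endpoint sentence in the same section spans the whole trial, and Section 7.2 carries no split. The separation is available but not applied to the percentages.

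**Relatedness is assessed.** Section 8.2 has the PI judge every event in relation to the study intervention. This is a real safeguard, and it could separate withdrawal from drug effects. Section 7.2 does not restrict the percentages to related events, however, and the judgement is made knowing the treatment.

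**Hypothesis 1b is descriptive.** Correct: it has no test or threshold, so no error rate is distorted. What suffers is the meaning of the comparison. How the comparison trials reported their events is not in the protocol, so the mismatch is shown only from this trial's side.

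**A stronger reading: the 10 mg and 25 mg doses are merged.** A reader might infer this because no per-dose summary is stated and the acute-course period in Section 3.2 holds both sessions. The protocol does not say it. Adverse-event and UKU review are scheduled separately at V3 and V4, so effects can be attributed to a dosing session from the data collected.

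**Conclusion.** The concern holds in a limited form. Collection from V1 is correct. The endpoint in Section 3.2, the reference state in Section 8.1 and the summary in Section 7.2, followed as written, place expected taper symptoms in the percentages that hypothesis 1b uses. Neither the three periods nor the relatedness judgement is carried into those percentages, and the definition of an adverse event conflicts with the collection window.

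The effect is confined to participants who tapered and were then dosed. The illustrative 28% to 44% in place of 20% rests on assumed rates and on independence. It shows that the excess could matter, not how large it will be. A reader should not conclude that withdrawal symptoms will be attributed to psilocybin, since relatedness is recorded, or that the doses are pooled. The point is worth correcting before the data are summarised, because it concerns a primary endpoint and needs no new data.

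**What to change.** 1. In Sections 3.2 and 7.2, tabulate adverse events and UKU items by onset interval: pre-dose (V1 to before V3); V3 to before V4; and V4 onward, with follow-up shown separately (for example V4 to V6, then after V6 to V9). Give the pre-dose interval its own column. The split at V4 also yields a per-dose view, which is a useful addition.
2. Base hypothesis 1b on events that are new or worse than the post-washout V2 rating.
3. Keep the all-period table beside it, and keep collection from V1 unchanged.
4. Reconcile the definition of an adverse event in Section 8.1 with the collection window, stating whether events before the first dose are adverse events.

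**Cost.** Wording changes and a wider table; visit-level UKU ratings and adverse-event reviews are already scheduled. Counts per interval will be smaller, which with 20 participants means wide uncertainty. A withdrawal symptom still raised at V2 could mask a drug effect when V2 is the reference, which is why the all-period table should be kept.
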